8.5. Laboratory Data

Analyses of laboratory assessments will be performed on subjects in each of the safety population utilizing the following rule: post-baseline data will include measurements occurring after the first DAC HYP dose date and during the 205MS303 Treatment Period. For subjects who were randomized to IFN β -1a in the 205MS301 study, this means that post-baseline data includes measurements occurring after the first DAC HYP dose date in the 205MS303 study. For subjects randomized to DAC HYP in the 205MS301 study, this means that post-baseline data includes measurements occurring during the 205MS303 studies on or after the first DAC HYP dose date in 205MS303. For subjects transitioned from the 205MS203 study or the 205MS302 study, this means that post-baseline data includes measurements occurring during the 205MS303 studies on or after the first DAC HYP dose date in 205MS303.

	Protocol 205MS303 Statistical Analysis Plan	Final Version 1.0
---	--	--------------------------

The following laboratory parameters will be included in the aforementioned analyses:

- Hematology:
 - White blood cell (WBC) parameters (as absolute values and as percentage of WBC): basophils, eosinophils, lymphocytes, monocytes, and segmented neutrophils
 - other hematology parameters: hematocrit, hemoglobin, Mean Corpuscular Hemoglobin (MCH), mean corpuscular hemoglobin concentration (MCHC), mean corpuscular volume (MCV), platelets, red blood cell (RBC) count, WBC
- Blood chemistry:
 - liver function tests (LFTs): alkaline phosphatase, alanine aminotransferase (ALT), aspartate aminotransferase (AST), gamma-glutamyl transpeptidase (GGT) and total bilirubin.
 - renal function tests and electrolytes: blood urea nitrogen (BUN), creatinine, bicarbonate, chloride, potassium and sodium.
 - thyroid function tests: total T4, and thyroid stimulating hormone (TSH).
- Urinalysis:
 - quantitative urinalysis parameters: pH and specific gravity
 - categorical urinalysis parameters: color and clarity, blood, glucose, leukocyte esterase, ketones, nitrite and protein.

Shifts to abnormally high or abnormally low values for quantitative parameters: Any subject with a non-high DAC HYP baseline (whether low, normal or unknown) will be counted in the risk set for shifts to high. Similarly, any subject with a non-low DAC HYP baseline result will be counted in the risk set for shifts to low. Shifts tables to the most extreme value in the 205MS303 Treatment Period (highest for shifts to high, lowest for shifts to low) will be conducted. The rationale for using the most extreme values or worst value is that should a treatment affect a laboratory value, that value could be affected at different times for different subjects. Therefore, the analyses present the most extreme values for each subject over time. For the 205MS301-303 safety population, the shift tables will be presented by previous treatment group of the 205MS301 study and for all subjects combined. For the 205MS203-303 safety population and 205MS302-303 safety population, the shift tables will be presented for all subjects combined within each of the safety population.

Shifts to abnormal values for categorical parameters: Any subject with a non-abnormal DAC HYP baseline (whether normal or unknown) will be counted in the risk set for shifts to abnormal. For the 205MS301-303 safety population, shifts from baseline to the most extreme post-baseline value will be presented by previous treatment group of the 205MS301 study and for all subjects combined. For the 205MS203-303 safety population and the 205MS302-303 safety population, the shift tables will be presented for all subjects combined within each of the safety population.

Descriptive summary statistics over time in the 205MS303 Treatment Period for quantitative parameters, of actual values, change from DAC HYP baseline (and when appropriate, percent change from baseline). These statistics may be displayed as figures. Time points analyzed will be based on protocol scheduled assessments and availability of data. Visit windows will be used to select the laboratory result used for each time point in the summary.

The number and percent of subjects with potentially clinically significant hematology laboratory abnormalities will be provided. The criteria of the potentially significant hematology laboratory abnormalities are provided below. Listing of lymphocytes for subjects with severe and prolonged lymphopenia defined as post DAC baseline lymphocytes $<0.5 \times 10^9$ cells/L consecutively for at least 6 months will be provided.

For the baseline thyroid function test parameters, descriptive summary statistics of actual values will be given. For urinalysis parameters, actual values will be listed.

Table 13: Criteria for Potentially Clinically Significant Hematology Abnormalities

Test	Criteria
White blood cell count (10^9 cells/L)	<3.0 ; ≥ 16.0
Lymphocytes (10^9 cells/L)	<0.8 ; <0.5 ; >12.0
Segmented neutrophils (10^9 cells/L)	≤ 1.0 ; <1.5 ; ≥ 12.0
Red blood cell count (10^{12} cells/L)	≤ 3.3 ; ≥ 6.8
Hemoglobin (g/L)	≤ 100
Platelets (10^9 cells/L)	≤ 100 ; ≥ 600

In addition, summary of baseline and worst post-baseline laboratory values categorized based on CTC (common toxicity criteria) grade, will also be presented for selected parameters of interest. The data may also be presented in graphs. The criteria for CTC grade for hematology parameters are provided below.

Table 14: Severity Grades for Hematology

Test	Grade 1	Grade 2	Grade 3	Grade 4
Hemoglobin (g/L)	[100, LLN)	[80, 100)	[65, 80)	<65
Lymphocytes (10^9 cells/L)	[0.8, LLN)	[0.5, 0.8)	[0.2, 0.5)	<0.2
Platelets (10^9 cells/L)	[75, LLN)	[50, 75)	[25, 50)	<25
Segmented neutrophils (10^9 cells/L)	[1.5, LLN)	[1.0, 1.5)	[0.5, 1.0)	<0.5
White blood cell count (10^9 cells/L)	[3.0, LLN)	[2.0, 3.0)	[1.0, 2.0)	<1.0

Additional Analyses of Liver Function Tests

For LFTs Alkaline phosphatase, ALT, AST, GGT and total bilirubin, additional categories will be defined to present baseline and post-baseline values (see table below). The incidence of ALT and/or AST elevations $>3X$ ULN by concurrently elevated bilirubin will also be summarized. ██████████

Table 15: Severity Grades for LFTs

Test	Grade 1	Grade 2	Grade 3		Grade 4
ALT	(1.0, 3.0)	[3.0, 5.0]	(5.0, 10.0]	(10.0, 20.0]	> 20.0
AST	(1.0, 3.0)	[3.0, 5.0]	(5.0, 10.0]	(10.0, 20.0]	> 20.0

Test	Grade 1	Grade 2	Grade 3	Grade 4
Alkaline phosphatase	(1.0, 2.5]	(2.5, 5.0]	(5.0, 20.0]	> 20.0
GGT	(1.0, 2.5]	(2.5, 5.0]	(5.0, 20.0]	> 20.0
Total bilirubin	(1.0, 1.5]	(1.5, 3.0]	(3.0, 10.0]	> 10.0

Grades determined by multiples of ULN. Grade 3 ALT and AST results will be subdivided as shown.

Plots of concurrent and non-concurrent peak bilirubin versus peak ALT or AST will be presented, as multiples of ULN on the log scale. Incidence of subjects experiencing total bilirubin at or above 2xULN and ALT or AST above 3xULN (either concurrent) will be summarized.

8.6. Subgroup analysis

Subgroup analysis, based on the DAC HYP baseline characteristics or usage of potential hepatotoxic medication, will be performed for the following selected safety endpoints for each of the three safety populations (the 205MS301-303 safety population, the 205MS203-303 safety population, and the 205MS302-303 safety population), over the 205MS303 Treatment Period.

Selected safety endpoints:

- Adverse event
- Serious adverse event
- Hepatic adverse event
- Serious hepatic adverse event
- Liver function test

The following DAC HYP baseline characteristics or usage of potential hepatotoxic medication are used to define subgroups if applicable:

- Age at DAC HYP baseline (age <50 versus age >=50)
- Pre-existing liver conditions at DAC baseline based on hepatic medical history report
- Taking potential hepatotoxic medication

For the potential hepatotoxic medication subgroup analysis, patients will be categorized as either without taking potential hepatotoxic medication or taking potential hepatotoxic medication. For patients taking potential hepatotoxic medications, they will be further categorized as either initiating first potentially hepatotoxic medication while on DAC HYP treatment or initiating first potentially hepatotoxic medication prior to DAC HYP treatment. Note that the list of potential hepatotoxic medications is defined and agreed by SABR prior to database lock.

Incidence of adverse events and serious adverse events will be summarized by DAC baseline age subgroup, and by system organ class and preferred term.

Summaries of hepatic events, as defined as an AE of special interest in Table 12, will be provided by subgroup for pre-existing liver conditions subgroup and potential hepatotoxic medication subgroup, respectively. In addition, incidence of hepatic events and serious hepatic events will be summarized by system organ class and preferred term for each of the subgroups of pre-existing liver conditions and potential hepatotoxic medication.

Summaries of maximum liver function test values will be provided by subgroup for both the pre-existing liver conditions subgroup and the potential hepatotoxic medication subgroup.

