6.4. Concomitant Therapy

Medications (prescribed or over-the-counter) and non-drug therapies are considered concomitant if they are used during the study (i.e., either started prior to the study and continued while on study or started after the first dose of study treatment). Medications started more than 180 days after the last dose of study treatment are not considered concomitant. The World Health Organization (WHO) dictionary will be used for coding concomitant medication, and the Medical Dictionary for Regulatory Affairs (MedDRA) will be used for coding concomitant non-drug therapies.

The number and percentage of subjects taking any concomitant medications in 205MS303 will be reported for the 205MS301-303 safety population, the 205MS203-303 Safety Population, and the 205MS302-303 Safety Population, respectively. The most frequent concomitant medications, defined as those taken by at least 10% of subjects, and use of alternative MS medications and steroids may also be summarized.

The list of potential hepatotoxic medications is defined and agreed by SABR prior to data base lock. The number and percentage of subjects taking any potential hepatotoxic concomitant medications in 205MS303 will be reported for the 205MS301-303 safety population, the 205MS203-303 Safety Population, and the 205MS302-303 Safety Population, respectively.

7. Efficacy Data

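### The hepatotoxic-medication subgroups in SAP 8.6 depend partly on drug starts during 205MS303, yet liver outcomes are counted over the whole treatment period, so outcomes that precede the drug are counted under taking

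*SAP*

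**What the plan says.** SAP section 8.6 defines three safety subgroups. Age and pre-existing liver conditions are fixed at DAC HYP baseline. The third is not: "patients will be categorized as either without taking potential hepatotoxic medication or taking potential hepatotoxic medication". Takers are divided further into those "initiating first potentially hepatotoxic medication while on DAC HYP treatment or initiating first potentially hepatotoxic medication prior to DAC HYP treatment".

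The outcomes are taken "over the 205MS303 Treatment Period", which section 5.3 runs from the first 205MS303 dose to 180 days after the last. For this subgroup, "incidence of hepatic events and serious hepatic events will be summarized by system organ class and preferred term". For laboratory data, "Summaries of maximum liver function test values will be provided by subgroup".

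No sentence in 8.6 orders the event or the LFT sample against the start of the medication, sets a landmark, or uses person-time. Section 8.2 includes adverse events by their relation to DAC HYP dosing only. Section 6.4 adds that "Medications started more than 180 days after the last dose of study treatment are not considered concomitant", so a drug started within those 180 days is concomitant.

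**The concern.** Membership of the taking group, of its started-while-on-DAC-HYP category and of the non-taker comparator depends partly on what happens after follow-up begins. Three consequences follow.

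- A hepatic event in year 1 is counted under taking if the subject's first hepatotoxic drug began in year 3. The same holds for an LFT peak.
- A subject must remain under observation to become a starter, so starters tend to be followed longer. Follow-up is unequal here: two cohorts enter at Week 144, dosing was closed on a calendar date, and subjects may stop early (SAP section 2; Table 4).
- A first start after the last dose is neither "initiating first potentially hepatotoxic medication while on DAC HYP treatment" nor "initiating first potentially hepatotoxic medication prior to DAC HYP treatment", so it has no category.

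Safety is the primary objective (section 1.1), hepatic events are of special interest (Table 12), and section 8.6 is where the SAP sets co-medication beside liver outcomes. A difference between these columns, or the lack of one, could come from the grouping alone.

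**Working it through.** **No plan figure to reproduce.** The SAP states no rate, power or sample size for this analysis. All rates below are assumptions.

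**Exact null calculation, hepatic events never ending follow-up.** Assume a hepatic event rate h = 0.04 per year, a first-start rate m = 0.25, 0.5 or 1.0 per year, independent exponential times, follow-up F uniform on 0.2-4.6 years, no drug effect and no prior users. Let L(a) be the mean of exp(-aF):

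L(a) = [exp(-0.2a) - exp(-4.6a)] / (4.4a)

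- Taker incidence = [1 - L(h) - L(m) + L(h+m)] / [1 - L(m)]
- Non-taker incidence = [L(m) - L(h+m)] / L(m)
- Share of takers' events before the drug = {[1 - L(m)] - [m/(m+h)][1 - L(m+h)]} / [1 - L(h) - L(m) + L(h+m)]

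For m = 0.25: L(0.04) = 0.90964, L(0.25) = 0.57690, L(0.29) = 0.53309.

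- Takers: 0.04655/0.42310 = 0.110
- Non-takers: 0.04381/0.57690 = 0.076
- Ratio: 1.45
- Share before the drug: (0.42310 - 0.40251)/0.04655 = 0.44

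For m = 1.0: L(1.0) = 0.18379, L(1.04) = 0.17567.

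- Takers: 0.08224/0.81621 = 0.101
- Non-takers: 0.00812/0.18379 = 0.044
- Ratio: 2.28
- Share before the drug: (0.81621 - 0.79263)/0.08224 = 0.29

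Simulation of the same set-up gives ratios of 1.44-2.31.

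**Letting hepatic events end follow-up.** Table 6 provides for permanent discontinuation because of elevated LFTs, and Table 5 puts the final visit 24 weeks after the last dose. The simulations therefore let a fraction of events end follow-up about six months later.

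| Follow-up assumed | No events end it | Half do | All do |
|---|---|---|---|
| Uniform 0.2-4.6 years (h 0.04; m 0.25-1.0) | 1.44-2.31 | 1.09-1.27 | 0.82-0.86 |
| Uniform 0.5-5.1 years (h 0.03 or 0.06; m 0.1 or 0.3) | 1.27-1.42 | 1.01-1.02 | 0.73-0.79 |
| Fixed 4 years (same h and m as row 2) | 1.0 | 0.67-0.79 | 0.46-0.60 |

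Entries are taker to non-taker incidence ratios; the true value is 1. Longer follow-up pushes the ratio up. Events that remove the chance of a later start push it down. The share of takers' events before the drug is 16-44% in row 1 and 16-49% in rows 2 and 3.

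**Adding prior users.** If 40% of subjects used such a drug before DAC HYP, the share falls to 17-20% of all takers' events with no early stopping.

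**Checking the remedy.** Splitting person-time at first use gives a rate ratio of 0.99-1.01 in all 24 scenarios of rows 2 and 3. That rests on a constant hazard. With a Weibull hazard, m = 0.5 and still no drug effect, the crude on/off ratio is 0.58-0.59 for shape 0.6 and 1.52 for shape 1.5, because exposed time falls later than unexposed time. The split therefore needs stratification by time since first dose.

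**The case against.** Several stronger readings are tempting, and the document does not support them.

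- *The grouping inflates the apparent risk of co-medication.* A ratio near 1.4-2.3 arises only if hepatic events do not shorten follow-up. The SAP provides for stopping because of LFTs, and the ratio then falls to about 1 or below. A real signal could equally be hidden.
- *The whole taking group is affected.* Users from before DAC HYP are defined at baseline, and a drug first started on DAC HYP in a parent study precedes every 205MS303 event. The fault lies in first starts within 205MS303. The SAP's split separates out the users from before DAC HYP, but its while-on-DAC-HYP category still mixes parent-study starts with 205MS303 starts.
- *Liver injury is attributed to the drug, or prompted its prescription.* Section 8.6 only promises summaries; section 5.4 calls the analyses generally descriptive. No test or ratio is specified, and nothing says that hepatic events led to such prescriptions.
- *A simple on/off split settles it.* A changing hazard biases that split too. Section 5.4 also imputes partial medication start dates to the earliest possible date, which would tend to place drugs before events.

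It is also fair to say that this is one descriptive subgroup analysis in an uncontrolled extension, and that the gap after the last dose is small. These points limit the size and importance of the finding. They do not remove it: the rule as written counts outcomes from before the drug under taking, whatever the table is used for. Section 7.2.1 shows that the SAP can use medication dates, since it censors relapse time at alternative MS medication.

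**Conclusion.** The concern holds for first starts within 205MS303, including all starts on DAC HYP among former IFN β-1a subjects. Hepatic events and LFT maxima from before such a start are counted under taking, and the compared groups have unequal follow-up. On the main assumptions (first row of the table) the null incidence ratio runs from roughly 0.8 to 2.3, with about 16-44% of takers' events preceding the drug. The less realistic case of equal four-year follow-up takes the ratio as low as 0.46. Prior users dilute the share of pre-drug events. The direction cannot be known in advance, so a reader of the table could not correct for it. Every figure rests on assumed rates, independent event and start times, and no drug effect. The counting fault itself follows from the text alone. The primary endpoints, incidence of adverse events and of serious adverse events, are unaffected.

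**What to change.** Amend section 8.6 as follows.

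1. Keep drugs first started before the first 205MS303 dose as a fixed subgroup, retaining the split between starts before DAC HYP and starts on DAC HYP in a parent study.
2. For first starts on or after that dose, count a hepatic event under taking only if its onset is on or after first use, and otherwise under not taking. Take LFT maxima separately from samples before first use and samples from first use onward.
3. Split person-time at first use and report hepatic events per 100 person-years in each state, stratified by time since first dose, for example by year. Use narrower bands early if risk is concentrated there.
4. State the category for first starts in the 180 days after the last dose.
5. Add a sensitivity analysis for partial medication start dates, for example placing them at the latest possible date instead of the earliest.

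The cost is SAP wording and modest extra programming with start dates already collected. The price is smaller cells, above all in the 205MS203 and 205MS302 cohorts, where stratified rates may be too sparse to show more than counts and person-years.

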8.7. Vital Signs

Vital signs collected in the 205MS303 study will be examined to determine the incidence of clinically relevant abnormalities. For each of the safety population, the number and percentage of subjects with clinically relevant post-DAC HYP baseline abnormalities in the 205MS303 study will be summarized. The definitions of abnormalities are provided in Table 16. For the purpose of determining shifts, DAC HYP baseline will be used. Summary statistics for actual values and change from DAC HYP baseline will also be presented.

For the 205MS301-303 safety population, the summary tables will be presented by previous treatment group of the 205MS301 study, and for all subjects combined. For the 205MS203-303 safety population and the 205MS302-303 safety population, the summary tables will be presented for all subjects combined within each safety population.

Table 16: Criteria to determine clinically relevant abnormalities in vital signs

Vital Sign	Shift	Criteria for Abnormalities
Temperature (°C)	Increase	>38°C and increase from baseline of at least 1°C
Pulse (bpm)	Increase	>120 beats per minute (bpm) if ≤120 bpm at baseline, or increase from baseline of more than 20 bpm
	Decrease	<50 bpm if ≥50 bpm at baseline, or decrease from baseline of more than 20 bpm
Systolic blood pressure (mmHg)	Increase	>180 mmHg if ≤180 mmHg at baseline, or increase from baseline of more than 40 mmHg
	Decrease	<90 mmHg if ≥90 mmHg at baseline, or decrease from baseline of more than 30 mmHg
Diastolic blood pressure (mmHg)	Increase	>105 mmHg if ≤105 mmHg at baseline, or increase from baseline of more than 30 mmHg;
	Decrease	<50 mmHg if ≥50 mmHg at baseline, or decrease from baseline of more than 20 mmHg

8.8. Physical Examination

A listing of subjects with change from normal to abnormal status in physical examination at any time during the 205MS303 study will be presented for each of the safety population.

8.9. Immunogenicity Data

Immunogenicity to daclizumab (i.e., anti-drug antibodies (ADAs) that bind to Daclizumab) will be assessed on all subjects in 205MS303 with available data. Positive samples will be further tested for neutralizing antibodies using a specific neutralizing antibody (NAb) assay. Results will be tabulated by nominal visit and overall.

For the 205MS301-303 safety population, the summary tables will be presented by previous treatment group of the 205MS301 study, and for all subjects combined. For the 205MS203-303 safety population and the 205MS302-303 safety population, the summary tables will be presented for all subjects combined within each safety population.

[REDACTED]

9. Pharmacokinetics and Pharmacodynamics

9.1. Pharmacokinetics

Blood serum will be collected at selected timepoints throughout the study to determine DAC HYP serum concentrations in order to monitor the drug trough level and [REDACTED]

[REDACTED]. Listings of DAC HYP plasma concentrations by subject will be presented for each of the safety population.

